### Bayesian Analysis

Bayesian statistics will be used to detect differences in treatment effects overall and in different patient subgroups. Models will be the same as in frequentist analyses (*i.e.*, GLMs with same covariates). For LOS outcomes, neutral priors centered at RR of 1.0 with 95% prior interval of 0.33-3.0 (0.5-2 for binary outcomes) will be used for the treatment effect (in the log RR scale, a Normal distribution with mean of 0 and variance of 0.57). A Normal (0, 10) prior will be used for the intercept term. Normal (0, 1) will be used for all other variables in the model. For sensitivity analyses, we will specify enthusiastic and skeptical priors based on the best published evidence (*i.e.*, Cochrane review). For all Bayesian analyses, we will report posterior medians and 95% credible intervals for group comparisons and probabilities of benefit or harm from the intervention.

**Feasibility:** From unpublished historical data from the Red Duke Trauma Institute from the calendar year 2017, approximately 300 patients matched these enrollment criteria. Accordingly, enrollment of 150-250 patients is expected over the course of the study.

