## BACKGROUND INFORMATION

Approximately 350,000 people suffer rib fractures in the United States each year, with more than one-third requiring hospitalization. Severe chest trauma may result in prolonged mechanical ventilation, post-traumatic pneumonia, long-term disability, and death. Morbidity and mortality increase with each fractured rib, and an inflection point seen at six or more rib fractures. Usual care typically consists of breathing exercises and pain control, often including opioids. However, despite usual care, rib fracture patients are more physically disabled at 30 days post-injury than a reference group of chronically ill patients and lose 70 days of work or usual physical activity.

An alternative to usual care is surgical stabilization of rib fractures (SSRF). Surgical stabilization of fractures is a well-established tenet of orthopedic surgery that is proven to facilitate bone healing, decrease the mobility of fractures, decrease pain, and improve mechanical function. Decreasing the mobility of fractured ribs has been shown to improve pain in small studies, and it may decrease the consumption of opioid pain medications. However, because the SSRF literature is plagued by industry bias and low-quality studies, the indications for the procedure remain unclear and it is rarely performed.

Evidence for SSRF in Flail Segments: In three small, randomized trials of patients with flail segments (radiographic findings of  $\geq 3$  consecutive ribs with  $\geq 2$  fractures), SSRF has been shown to decrease the duration of mechanical ventilation, the incidence of pneumonia, the duration of intensive care, and overall medical costs. Similarly, recent systematic reviews and meta-analyses of these studies have supported the reduction in duration of mechanical ventilation, pneumonia, and tracheostomy. However, these trials and meta-analyses are limited by study heterogeneity, narrow inclusion criteria, and small sample sizes ( $n < 50$ ). For these reasons, SSRF has not been widely adopted in the flail segment population.

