**Secondary Outcomes (Patient-Centered Outcomes):**

- Health status at 30 days, 3 months, and 6 months as measured by the EuroQol-5D-5L
- Time from injury to return to work or usual activity (days)
- Time from injury to resolution of pain (days)

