### Frequentist Analysis

Generalized linear models (GLMs) will be used to analyze all outcomes and will include treatment group and unit of admission (stratifying variable) as covariates. For LOS outcomes, negative binomial or zero-inflated negative binomial (for outcomes with large number of zeros; *e.g.*, ventilator days, ICU days) regression models will be used. Binary outcomes will be analyzed with log binomial regression models to estimate relative risks (RRs). For longitudinal outcomes, we will use mixed models including treatment group, time, and center as covariates and a random intercept (and slope if needed) for subject. We will report RRs or group differences and 95% confidence intervals for all outcomes.

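### The Bayesian intercept and covariate priors suit log-scale models but not secondary outcomes analysed as raw-scale differences, for which no treatment prior is stated

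*Combined protocol and SAP*

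**What the plan says.** The Frequentist Analysis section opens broadly: "Generalized linear models (GLMs) will be used to analyze all outcomes and will include treatment group and unit of admission (stratifying variable) as covariates". It then specifies "For LOS outcomes, negative binomial or zero-inflated negative binomial" regression, and log binomial models for binary outcomes. For repeated measures it says: "For longitudinal outcomes, we will use mixed models including treatment group, time, and center as covariates". Results are to be reported as relative risks or as group differences. No family or link is given for continuous outcomes.

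The Bayesian Analysis section says "Models will be the same as in frequentist analyses". It then gives, in this order:

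- a neutral treatment prior on the log relative-risk scale, with one 95% interval for length of stay (0.33 to 3.0) and one for binary outcomes (0.5 to 2);
- for the constant: "A Normal (0, 10) prior will be used for the intercept term";
- for the rest: "Normal (0, 1) will be used for all other variables in the model".

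No treatment prior is given for an outcome analysed as a difference. The section does not say that outcomes are centred or scaled, or whether 10 is an SD or a variance. Probabilities of benefit or harm are promised for all Bayesian analyses.

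The outcomes not covered by a log-scale treatment prior are continuous opioid use, EQ-5D-5L health status, and the two times from injury (return to work or usual activity, and resolution of pain). The Hypothesis section names all of these.

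**The concern.** A prior has the units of its coefficient. On a log scale, Normal(0, 1) allows rate ratios from about 0.14 to 7 (exp of ±1.96), which is generous. On a raw scale it says that a unit or time effect lies within about 2 days, 2 points or 2 MME.

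A zero-centred prior on the intercept says that the control mean is near zero, which is implausible for days to return to work or a 0-100 score. If the intercept is pulled down while treatment is free to move, the treatment coefficient takes up the gap and a difference appears that is not in the data.

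The estimates at stake are the Bayesian ones for the outcomes in the trial's own hypothesis. The Limitations section also says that the Bayesian analysis will be done regardless if recruitment is low, which is when priors weigh most.

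**Working it through.** **1. The plan's own prior figure.** A 95% interval of 0.33 to 3.0 needs SD = ln(3.0)/1.96 = 0.561, so a variance of 0.314. The plan states a variance of 0.57. That variance gives an interval of 0.23 to 4.39, while an SD of 0.57 gives 0.33 to 3.06. So 0.57 fits the interval only as an SD, and whether the 10 in the intercept prior is an SD or a variance is a real question.

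**2. Log-scale models are not affected.** The sample-size section assumes a control median of 10 days (IQR 6-15). On the log scale, SD = ln(15/6)/1.349 = 0.679, and with 75 per arm the SE of the treatment effect is 0.679 × √(2/75) = 0.111. The weight on the data is v/(v + SE²), where v is the prior variance:

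- v = 0.314: weight 0.96
- v = 0.57: weight 0.98
- v = 1: weight 0.99

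An observed ratio of 0.70 becomes 0.703 to 0.709. The intercept prior is also harmless. By the formula in step 3, with ln(10) = 2.303, SD²/n = 0.679²/75 = 0.00615 and v = 10, the spurious log ratio is 2.303 × 0.00615/10.00615 = 0.0014.

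**3. Raw scale, intercept prior alone.** Assume an identity link, treatment coded 0/1, a flat treatment prior, known residual SD and no true difference. The control arm alone informs the intercept, so its posterior mean is m × v/(v + SD²/n). The treated mean is fitted freely. The spurious difference is therefore

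m × (SD²/n) / (v + SD²/n),

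with m the common mean, n the number per arm, and v = 100 if 10 is an SD or 10 if it is a variance. The documents give no SDs for these outcomes. The 70 days is a background figure (patients "lose 70 days of work or usual physical activity"), not a design input. The other means and all SDs are assumptions.

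For return to work with SD 40 and n = 75, SD²/n = 21.33. Then 70 × 21.33/121.33 = 12.3 days (10 an SD), and 70 × 21.33/31.33 = 47.7 days (10 a variance). Adding a balanced two-level unit term with its Normal(0, 1) prior changes these to 12.3 and 47.3. Results with the unit term:

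| Outcome (assumed mean, SD) | 75/arm, 10 = SD | 75/arm, 10 = variance | 125/arm, 10 = SD |
|---|---|---|---|
| Return to work, days (70, 40) | +12.3 | +47.3 | +7.9 |
| MME/day (50, 40) | +8.8 | +33.8 | +5.7 |
| 0-100 score (70, 20) | +3.5 | +24.0 | +2.2 |
| EQ-5D index (0.7, 0.2) | 0.0 | 0.0 | 0.0 |

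Range over other assumed SDs, 75 per arm, 10 as an SD, from the formula:

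- return to work, SD 30 to 60: 70 × 12/112 = 7.5 to 70 × 48/148 = 22.7 days
- MME/day, SD 20 to 60: 50 × 5.33/105.33 = 2.5 to 50 × 48/148 = 16.2
- 0-100 score, SD 15 to 25: 70 × 3/103 = 2.0 to 70 × 8.33/108.33 = 5.4 points

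The sign is always positive. SSRF would look worse for days and MME, and better for the health score. For return to work at SD 40 the posterior SD is 6.2, so the spurious +12.3 is about two posterior SDs from zero. A true 14-day reduction would appear as −14 + 12.3 = −1.7 days, or as −14 + 47.3 = +33.3 if 10 is a variance.

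**4. The other reading: Normal(0, 1) also covers treatment.** With the treatment coefficient taken alone, the data weight is 1/(1 + SE²), with SE = SD × √(2/n). At 75 per arm:

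- score, SD 20: SE 3.27, weight 0.086, so 8 points becomes 0.69
- return to work, SD 40: SE 6.53, weight 0.023, so 14 days becomes 0.32

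Over score SDs of 15-25, MME/day SDs of 20-60, return-to-work SDs of 30-60 days, and 75-125 per arm, the weight runs from 0.01 to 0.22.

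**The case against.** A reader might infer that the plan puts Normal(0, 1) on treatment for these outcomes, so that the trial would report almost no effect whatever it observes. The text does not support that. The sentence follows separate priors for treatment and intercept, so its natural reach is the remaining terms: unit, time and center. The treatment prior for continuous outcomes is therefore unstated, and step 4 holds on one reading only. On the natural reading the distortion is a shift, not uniform shrinkage.

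A reader might also infer that every outcome measured in days is exposed, including the primary. That is not so. Hospital length of stay has a negative binomial model and its own log-scale prior, and step 2 shows the data dominate. An EQ-5D index near 0-1 is safe as well, and the plan does not say whether the index or the 0-100 item is the endpoint.

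Other points also stand. The identity link is inferred from the mention of group differences. The Bayesian section describes the reused models as GLMs with the same covariates, so its reach to the mixed models is an inference too. If treatment were coded symmetrically about zero with balanced arms, the intercept prior would not move the treatment effect, and the plan states no coding. With 10 as an SD, the effect on a 0-100 score is modest. Frequentist estimates and intervals will be reported alongside, so the Bayesian results would not stand alone.

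None of this removes the point. The intercept and covariate priors are stated without limit, and a statistician who applied them to a raw-scale outcome in an ordinary 0/1-coded model would get a biased answer.

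**Conclusion.** The point holds for secondary outcomes analysed on an additive raw scale: continuous MME, the 0-100 health item if it is the endpoint, and the two time-from-injury outcomes if modelled as means. It does not hold for the length-of-stay outcomes, the binary outcomes or a 0-1 index.

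It is more than missing detail, because a stated rule gives a wrong result where it is applied. The size runs from small (about 2 points on the score at 125 per arm) to serious (about 12 days at 75 per arm) if 10 is an SD, and is severe for all three outcomes if 10 is a variance. These figures rest on the assumed means and SDs, identity link, 0/1 coding, flat treatment prior and two-level unit. They come from a single-time-point Gaussian model with known residual SD; the mixed model was not simulated. The change should be made before the Bayesian analyses are run.

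**What to change.** In the Bayesian Analysis section:

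- Limit the stated treatment, intercept and covariate priors to the log-link models.
- For each outcome analysed on an additive scale, state family and link, and say which EQ-5D-5L quantity is the endpoint. If the two time-from-injury outcomes are not to be modelled as means, say so here and give priors for that model.
- Centre each such outcome and divide it by its pooled SD before fitting. Alternatively, centre the intercept prior on the sample mean with an SD scaled to the outcome. Normal(0, SD 1) is then a weak prior for unit and time.
- Give an explicit neutral treatment prior in SD units, for example Normal(0, SD 0.5 to 1). The exact value is the authors' choice. The data weight SD₀²/(SD₀² + 2/n), with SD₀ the prior SD, is 0.25/(0.25 + 0.0267) = 0.90 for SD 0.5 and 1/1.0267 = 0.97 for SD 1 at 75 per arm, whatever the unit. With the outcome centred and no true difference, the spurious difference is zero.
- Write every prior with 'SD =' or 'variance =', and reconcile 0.57 with its stated interval.

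The cost is a paragraph of SAP wording. Data collection, sample size and the primary frequentist analysis do not change.

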## **ETHICS**

Written informed consent will be obtained from each patient prior to enrollment. In the event, the patient is unable to provide informed consent, the LAR or family member will be approached to provide consent for the patient. An assent form will be provided to those subjects 16 and 17 years of age. A member of the study team will discuss the trial details to the patient and/or LAR/family member and will allow them time to make a decision regarding participation.

#### **DATA HANDLING AND RECORD KEEPING**

All data will be reviewed and entered into a RedCap database managed by UTHealth. Each subject will be assigned a study specific number once they have signed consent and been enrolled into one of the three study arms. Data utilized for this trial will be obtained from the subject's medical records and the MHH-TMC trauma registry.

All hard copy data will be kept in a secure, locked office and all electronic documents will be kept on password-protected computers accessible to only personnel directly involved with this trial.

#### **QUALITY CONTROL AND ASSURANCE**

Each item on the web forms will have validity checks performed to ensure that the data entered are accurate and that items are not skipped during entry by mistake. Checks will be developed by both clinical investigators and research assistants. Depending on the question, any item found that does not meet the respective edit criteria will have an appropriate error message displayed when the user tries to save the data. Errors will be classified as either "hard" errors meaning that a valid response is required before the data can be saved or as "soft" errors in which the entry operator can either correct the errors or override them to indicate that the data are correct although it does not meet the edit criteria. Examples of hard errors would be items such as identifiers and event dates. An example of a soft error would be values that are outside a pre-defined range.

When the data record is saved, a form status field will be updated to indicate the status of the form. There are currently four status states that the form can have. These statuses are: the form is incomplete, the form is complete, the form was saved with errors, and the form is complete with errors. For the first status, the entry user will have the option to save a record as —incomplete for situations where they have partially entered a form and must stop because of an interruption. This will allow the user or the study coordinator to pull up the form at a later time and finish completing it. If the form was entered without any errors, then the record will be saved as complete. If the user overrides any soft errors found, the record will be saved as —saved with errors.

#### **PUBLICATION PLAN**

The final clinical trial protocol will be formulated into a manuscript for pretrial publication. The results of the study will be published at internal meetings and used to inform the management of patients with rib fractures at the Red Duke Trauma Institute. Publication of the results of the trial will be sought in a peer-reviewed journal (intended: *JACS, J Trauma Acute Care Surg*). Presentation at a national meeting (AAST, EAST, WTA, or ACS) is also intended.

## ATTACHMENTS

Appendix A. EuroQOL-5D-5L tool.

### EuroQOL-5D-5L at 1, 3 and 6 months

#### Mobility

- I have no problems walking
- I have slight problems walking
- I have moderate problems walking
- I have severe problems walking
- I am unable to walk

#### Self-Care

- I have no problems washing or dressing myself
- I have slight problems washing or dressing myself
- I have moderate problems washing or dressing myself
- I have severe problems washing or dressing myself
- I am unable to wash or dress myself

#### Usual Activities

- I have no problems doing my usual activities
- I have slight problems doing my usual activities
- I have moderate problems doing my usual activities
- I have severe problems doing my usual activities
- I am unable to do my usual activities

#### Pain

- I have no pain or discomfort
- I have slight pain or discomfort
- I have moderate pain or discomfort
- I have severe pain or discomfort
- I have extreme pain or discomfort

#### Anxiety)

- I am not anxious or depressed
- I am slightly anxious or depressed
- I am moderately anxious or depressed
- I am severely anxious or depressed
- I am extremely anxious or depressed

“Your Health Today” (0-100)

Are you back to work or usual physical activity? (yes/no)

If yes, when?

Has your rib pain completely or almost completely resolved? (yes/no)

If yes, when?

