## ABSTRACT

**BACKGROUND:** Rib fractures are the most common injury in blunt thoracic trauma and are a major source of morbidity and mortality. In severe cases, usual care with pain medications is often insufficient to prevent respiratory failure, pneumonia, and tracheostomy. Additionally, patients may go on to have pain that far exceeds their hospitalization and limits their ability to return to work. Surgical stabilization of rib fractures (SSRF) is a promising intervention that may decrease morbidity and time to return to work.

**PROBLEM:** Few high-quality studies have been performed that compare SSRF to usual care. Of these, even fewer have considered patient-centered outcomes following discharge. Furthermore, SSRF is often performed late as salvage therapy rather than early as a preventative intervention.

**STRATEGY:** To address this gap in knowledge, we propose to perform a randomized trial with a parallel observational arm of blunt trauma patients with multiple rib fractures comparing the effectiveness of early SSRF to usual care on clinical and patient-centered outcomes. The primary endpoint is hospital length of stay. Secondary endpoints will include clinical outcomes (incidence of respiratory failure, pneumonia, tracheostomy, mortality) and patient-centered outcomes (health status and time to return to work).

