## GOAL AND SPECIFIC AIMS

Aim 1: Compare the effectiveness of SSRF to usual care alone on traditional clinical metrics and patient-centered outcomes.

Aim 2: Evaluate for heterogeneity of treatment effect in high-risk subgroups.

Aim 3: Determine the impact of multiple rib fractures on post-discharge health status and time to return to work or usual physical activity.

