## HYPOTHESIS

Patients with severe chest trauma who undergo SSRF will have decreased rates of opioid consumption as measured in morphine milligram equivalents per day. Patients with severe chest trauma who undergo SSRF will also have improved health status (as measured by the EuroQOL-5D-5L) at 30 days and 3 months, earlier return to work or normal physical activity, and decreased time from injury to resolution of chest wall pain.

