### Data Collection

The clinical research staff will follow the subjects throughout their hospitalization (or up to 30 days, whichever comes first) for complications such as surgical site infections, pneumonia, need for reoperative procedures and other complications commonly associated with rib fractures.

The data will be reviewed and entered into the UT Redcap database. Each subject will be assigned a study specific number. The subject's medical record and the MHH-TMC trauma registry will be utilized for data collection purposes. Data will be collected until discharge or 30 days (whichever occurs first) and questionnaires will be conducted up to 6 months post ED admission.

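### Return to work is listed as a secondary endpoint, but the one either/or question with one unlabelled date cannot estimate it, and it leaves open which milestone is dated

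*Combined protocol and SAP*

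**What the plan says.** The endpoint appears under several descriptions.

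- **Abstract**, list of secondary endpoints: "patient-centered outcomes (health status and time to return to work"). Work stands alone here.
- **Goal and Specific Aims**, Aim 3: "time to return to work or usual physical activity".
- **Hypothesis**: "earlier return to work or normal physical activity".
- **Secondary Outcomes (Patient-Centered Outcomes)**: "Time from injury to return to work or usual activity (days").
- **Appendix A**, the measuring item: "Are you back to work or usual physical activity? (yes/no"), followed by a single request for the date if the answer is yes.

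The item is asked with the "EuroQOL-5D-5L at 1, 3 and 6 months", and Data Collection states that "questionnaires will be conducted up to 6 months post ED admission". Appendix B contains no employment status before injury, no work-specific item and no work date. Limitations states that the staff who administer the questionnaire cannot be blinded. No power or effect size is given for this outcome.

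**The concern.** A patient who has resumed usual activity but is still off work answers yes. So does a desk worker who is back at work but not yet physically active. Where both have happened on different days, nothing says which date to record. Nothing says how a patient without a job should answer either, and eligibility runs from age 16 with no upper limit, so such patients will be enrolled.

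Two things are at stake. First, whatever the item shows, nobody can say from the listed data whether patients went back to work sooner, which is the claim that the Abstract sets up. Second, the choice between two candidate dates falls to people who know the allocation.

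**Working it through.** **1. Can return to work be recovered from the listed data?** It would need (a) who was working before injury and (b) a date tied to work. Appendix A gives one date for either event, and Appendix B gives neither (a) nor (b). The EuroQol usual-activities question is scored separately at each interview, but it carries no date and does not isolate work. So the answer is no, whatever the effect size.

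**2. Is there a figure in the plan to reproduce?** Not for this outcome. The only power statement concerns hospital length of stay and does not bear on the point. The one related figure is in Background Information, where patients "lose 70 days of work or usual physical activity". That is itself a combined figure.

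**3. How much could a work effect be diluted? Closed form.** Assume independent exponential times, everyone employed and the earlier date recorded. Let r be the activity rate divided by the work rate. Then

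HR(combined) = (HR_work + r × HR_act) / (1 + r), and share kept = ln HR(combined) / ln HR_work.

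With HR_work = 1.5 (ln 1.5 = 0.405):

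| HR_act | r | HR(combined) | Share of log HR kept |
|---|---|---|---|
| 1.0 | 0.5 | (1.5+0.5)/1.5 = 1.33 | 71% |
| 1.0 | 1 | (1.5+1)/2 = 1.25 | 55% |
| 1.0 | 2 | (1.5+2)/3 = 1.17 | 38% |
| 1.0 | 3 | (1.5+3)/4 = 1.13 | 29% |
| 1.25 | 0.5 to 3 | 1.42 to 1.31 | 86% to 67% |
| 1.5 | any | 1.50 | 100% |

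**4. Simulation with non-workers included.** Assumed, not from the documents: HR_work 1.5; median 90 days to work; median 45, 70 or 90 days to activity; 50, 70 or 90% employed; correlation 0.5 or 0.9. The follow-up of 180 days reflects the six-month interviews. The sample sizes of 150 and 250 and the two-sided 0.05 level are the plan's. Non-workers contribute the activity date. Cox models were used, as a convenient yardstick; the plan names generalized linear models for all outcomes.

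| HR_act | Log HR kept, earlier date recorded | Log HR kept, workers report work |
|---|---|---|
| 1.0 | 5-57% | 49-94% |
| 1.25 | 56-76% | 75-98% |
| 1.5 | 92-102% | 92-105% |

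Power of the combined outcome under the earlier-date rule is 6-25% (N=150) and 5-38% (N=250) at HR_act 1.0, and 57-66% and 80-88% at HR_act 1.5. A work item analysed in the employed recovers an HR of about 1.5, with power 34, 45 and 58% (N=150) and 53, 66 and 79% (N=250) at 50, 70 and 90% employed. So when the benefit is shared equally, the combined outcome is more powerful at 50 or 70% employed and about level at 90%, because every patient contributes.

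**5. The reverse case.** Here treatment speeds activity only (HR 1.5), work is unchanged, the median to work is 70 days, the median to activity is 45 or 70 days, the correlation is 0.5, and 50 or 70% are employed. A log-rank test on the earlier date is then significant in favour of surgery in 36-56% of trials (N=150) or 57-76% (N=250). This is a true effect on the combined outcome. It becomes misleading only if labelled as return to work.

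**The case against.** The strongest reply is that outcome and instrument agree. Aim 3, the hypothesis, the formal outcome list and the item are all either/or, and only the Abstract shortens this to work. On that view the defect is loose shorthand on an unpowered secondary outcome, and rewording the Abstract would cure it. Much of this stands: the formal list does not promise a work-only endpoint, and rewording would remove the contradiction. It would not say which date to record or how non-workers should answer, and it would give up an outcome that the Abstract uses to motivate the trial.

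A reader might infer that the single item loses most of any real work effect. The documents do not support that. It requires surgery to speed work while leaving activity untouched, and in most settings also the earlier date to be recorded. The hypothesis predicts benefit on work or activity together, with earlier pain resolution. The documents give no employed share, no separate times and no effect size.

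A reader might also infer that interviewers will bias the date. The plan already acknowledges the lack of blinding, and no size can be put on such a bias. Splitting the item removes the choice between dates but not biased reporting in general.

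**Conclusion.** The measurement gap follows from the text alone: the Abstract's endpoint cannot be estimated from the listed data, and the combined outcome has no dating rule and no rule for non-workers. The dilution is conditional. Under the earlier-date rule with a work HR of 1.5, it ranges from severe when activity is unaffected to essentially none when activity benefits equally. The simulated ranges also take activity to resume no later, at the median, than work; the closed form shows less loss (71% kept at r = 0.5) when activity comes later. This is a worthwhile and cheap improvement to a secondary outcome. It does not touch the primary analysis.

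**What to change.** In Appendix A, replace the single item with two: (a) whether the patient was working before the injury and, if so, whether and on what date they returned to work; (b) whether and on what date they returned to usual physical activity.

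Keep the combined outcome in the formal list, defined as the earlier of the two dates, or the activity date for those not working before injury. Report return to work in those working before injury as a separate estimate, stated in advance to be less powerful. Use one wording in the Abstract, Aim 3, the Hypothesis, the secondary outcome list and Appendix A, and add the new fields to Appendix B.

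The cost is two or three extra questions in interviews already planned at 30 days, 3 months and 6 months, and a work-only interval that rests on fewer patients. Anyone interviewed before the change would need re-contact, with the recall error that brings.
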